# II. Research Plan and Design

- **A. Study Objectives:** To see if heat therapy can be used to improve metabolic symptoms and peripheral nerve mitochondria, leading to improvements in sensory function.
- **B. Study Type and Design:** This prospective, observational cohort pilot study will recruit 20 patients with prediabetes with or without peripheral neuropathy (painful and non-painful) to participate in a 4-week heat therapy intervention. After screening, informed consent, and enrollment into the study, subjects will undergo a pre-intervention evaluation that will assess metabolic biomarkers and heat shock protein levels (blood), peripheral neuropathy, and epidermal evaluation (skin biopsy). After the skin biopsy has the appropriate time to heal (approximately 7-14 days), the subjects will undergo 45-minute heat treatments in 40°C water, three times weekly, for 4 weeks. After completion of heat treatments, subjects will undergo a repeated post-intervention evaluation and skin biopsy. Statistical approaches will compare pre– and post-heat therapy measures.

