Visit 2 (pre-intervention evaluation): Once inclusion and exclusion criteria are confirmed by laboratory results, the presence and type of neuropathy will be confirmed with a clinical examination and nerve function testing (Drs. [name] or [name], approx. 1.5 hours).

Neuropathy and Pain Assessment: medical evaluation by Drs. [name] and [name], Utah Early Neuropathy Scale (UENS), Quantitative Sensory Testing (QST). Questionnaires: Brief Pain Inventory (BPI), PROMIS Physical Function short form. Skin Biopsy: Patients will undergo a punch skin biopsy from the proximal thigh. Total dermal and epidermal innervation will be quantified from skin biopsies. The punch skin biopsy will be performed using a 3 mm disposable circular punch (Miltex, York, PA) after injection of 2% lidocaine under a sterile technique. No suture will be used. The skin will be placed in freshly prepared Zamboni's fixative for one hour. The tissue will be sectioned at 50 µm and processed for immunohistochemistry using rabbit anti-PGP9.5 primary antibody (1:3000; Chemicon, Temecula, CA). Sections will be coded in order to carry out the analysis in a blinded fashion and quantified. The biopsy will be used for quantification of GLO1 enzymatic activity.

Visits 3-14 (heat therapy intervention x 12 treatments): After the skin biopsy has appropriate time to heal (approximately 7-14 days), the subjects will undergo 30-minute heat treatments in 40°C water, three times weekly, for 4 weeks (approx. 1 hour each).

[figure not shown]
Subjects will be immersed up to the shoulder in a 40°C hot tub until rectal temperature  $(T_{re})$  increases by 1°C (~20 minutes). Subjects will then remain in the water bath submerged to waist level to maintain Tre between 38.5 and 39.0°C for another 30 minutes (approx. total time submerged ~50 minutes). Following hot water immersion, subjects will be monitored for another 10 min, or until Tre falls below 38.5°C. Core temperature will be monitored using either 1) a rectal probe with sterile disposable sheaths or 2) a sterile disposable rectal thermistor probe (401 A/C, Advanced Industrial Systems, Inc., Harrods Creek, KY) to be inserted  $\sim 1$  inch past the anal sphincter

(inserted by participant). Heart rate and blood pressure will be monitored throughout the treatment. Subjects will be continually monitored and removed from the hot bath if  $T_{re}$  exceeds 39.5°C.

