**Visit 15 (post-intervention evaluation)**: After completion of heat therapy intervention, subject will return to assess any change in fasting laboratory tests, oral glucose tolerance test, and questionnaires as listed in Visit 1 (approx. 2.5 hours). In addition to the two questionnaires completed at Visit 1, subject will also complete a Patient Global Impression of Change (PGIC) survey (included in appendix). A single question asks patients "After my treatment, my pain is:" with a 7-point scale ranging from -3 (very much worse) to 0 (no different) to +3 (very much improved). This measure will be a secondary determinant of analgesic response to treatment and will only be administered at the completion of heat therapy intervention

**Visit 16 (post-intervention evaluation)**: Subject will return for a final visit to assess any change in the presence or type of neuropathy by completing the same clinical examination and nerve function testing as in Visit 2 (Drs. [name] or [name], approx. 1.5 hours).

- 3. All procedures will be performed solely for research purposes. None should be considered standard of care or billed to insurance.
- 4. Blood will be processed at the CTSU and sent to Quest Diagnostics for resulting. Subjects will have the option to save leftover samples for future deidentified research. Otherwise, any leftover samples will be destroyed. Skin biopsy samples will be housed at the University of Kansas Medical Center in a secure laboratory for processing. Only the study team will have access to any samples. All samples will be marked only with subject ID and date.
- 5. Timeline:

Subjects are expected to complete the study in approximately 11-13 weeks.

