# L. Assessment of Subject Safety and Development of a Data and Safety Monitoring Plan

- 1. Elements of the plan include:
  - a. Persons/groups who will review the data (study team; independent safety monitor, data monitoring committee or formal DSMB): The PI or Co-Is will monitor AEs monthly, grade them, and indicate if the AE is related to the study procedure (definite, probably, possible, unlikely, not related). For each AE, the PI will determine if the study procedure should be continued. Patients will be instructed to call the PI's office (or on-call resident/coordinator if at night or on the weekend) to report events that occur between study visits. All SAEs will be reported to the HSC and Clinical Research Center (if applicable) and FDA guidelines, as soon as possible, but no later than five working days.
  - b. Data/events that will be reviewed: Any serious adverse events (SAE) will be reviewed as soon as possible and reported to the IRB if applicable.
  - c. Frequency of review: Data safety will only be monitored if necessary (unusually high frequency of adverse events (AE) or at any SAE).
  - d. Types of analyses to be performed: N/A
  - e. Safety-related triggers that would cause the PI to stop or alter the study: N/A -Study activities are considered low risk and any adverse symptoms will be treatment promptly, including temporary removal from heat treatment. Will assess if further safety-related triggers need to be identified as needed.
- 2. Nursing staff will continually monitor participants for adverse events. Any adverse event will be immediately reported to the PI and study coordinator per KUMC Human Subject Committee reporting policies. AEs will be classified as follows: related to study procedure as determined by the PI or unrelated to study procedure (related instead to underlying disease, pre-existing conditions, or other factors), anticipated (included in consent form) or unanticipated (not included in consent form), serious (SAE, Grade 4 using CTCAE v3.0) or not serious (AE, Grade 1, 2 or 3 using CTCAE v3.0)
- AEs that are not related to study procedures or are otherwise considered anticipated, low-risk events (ie: bruising or bleeding at injection site) will be monitored and recorded, but not necessarily reported to the medical monitor or the HSC unless frequency of event is considered unanticipated.

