Any AEs that are related to study procedure, are unanticipated, and are considered serious will be reported to the medical monitor and to HSC. A report that summarizes the frequency of all AEs will be provided to the medical monitor as needed. If a patient experiences a serious adverse event, they will be discontinued from the study.

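### A serious adverse event removes the participant from the study and not only from heat, so post-treatment values are lost that could often still be collected

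*Combined protocol and SAP*

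**What the plan says.** The rule closes the adverse-event text of II.L: "If a patient experiences a serious adverse event, they will be discontinued from the study". The same section defines the trigger as "serious (SAE, Grade 4 using CTCAE v3.0" and classifies relatedness separately, so an unrelated Grade 4 event also triggers it.

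Other parts of II.L bear on how to read the rule:

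- It allows a participant with adverse symptoms to be taken out of heat for a time. The plan can therefore separate stopping heat from leaving the study.
- It lets the PI decide, after each adverse event, whether the study procedure goes on.
- It provides for review ("Data safety will only be monitored if necessary (unusually high frequency of adverse events (AE) or at any SAE") and for reporting ("Any adverse event will be immediately reported to the PI and study coordinator per KUMC Human Subject Committee reporting policies").

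The schedule fixes what is lost:

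- II.E gives heat at "Visits 3-14 (heat therapy intervention x 12 treatments".
- II.B places the repeat biopsy after heat: "After completion of heat treatments, subjects will undergo a repeated post-intervention evaluation and skin biopsy".
- II.E describes Visit 15 in the same way: "After completion of heat therapy intervention, subject will return to assess any change in fasting laboratory tests".
- Visit 16 consists of "completing the same clinical examination and nerve function testing as in Visit 2".

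V.A names fasting glucose and IENF density, before and at the end of treatment, as the two primary outcomes. It tests change with a paired t-test and takes both values to be available for every patient. None of the text supplied provides an early-termination visit or outcome collection after removal.

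**The concern.** Stopping heat after a Grade 4 event is not in dispute. The question is why the participant should also leave the study. Visits 15 and 16 give no heat. For someone who has finished all 12 sessions, removal takes away measurements and spares no heat exposure.

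Two stated purposes are touched. I.A includes safety among the aims, and II.C says that the pilot is to supply the effect size for a larger study. If heat caused the event, the post-treatment value is missing because the participant tolerated heat badly, and the mean change then describes those who tolerated it. An unrelated event costs precision but does not select in that way.

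There is also a point of clarity. II.L requires serious events to be reviewed and reported, but it does not expressly require an event to be followed to its outcome once the participant has been removed.

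**Working it through.** The plan gives no serious-event rate, standard deviation, significance level or power, so it has no figure to reproduce. The check traces the rule through the schedule and then sizes the loss.

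**Step 1. What is lost, by timing of the event**

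| Event falls | Lost | Source of the loss |
|---|---|---|
| Before Visit 3 | No heat effect (no heat given yet) | – |
| Visit 3 to session 12 (Visit 14) | Post-treatment fasting glucose and IENF density | II.L together with II.B and II.E, which tie the post-treatment evaluation to completion of heat |
| After session 12, before Visit 15 | Both primary post-treatment values | II.L alone |
| Between Visits 15 and 16 | Visit 16 neuropathy measures, and the biopsy if not yet taken; fasting glucose is kept | II.L alone |

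The Visit 16 text does not name the biopsy. II.B puts it after heat, so either visit fits the table.

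**Step 2. How often the rule might apply**

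Inputs: 20 participants (II.C) and an assumed risk p of a serious event per participant. Chance of at least one = 1 − (1 − p)^20; expected number = 20p.

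| Assumed p | At least one of 20 | Expected number |
|---|---|---|
| 0.5% | 1 − 0.995^20 = 9.5% | 0.1 |
| 1% | 1 − 0.99^20 = 18.2% | 0.2 |
| 2% | 1 − 0.98^20 = 33.2% | 0.4 |
| 5% | 1 − 0.95^20 = 64.2% | 1.0 |

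These are upper bounds on the chance of losing both primary values because they count events at any time. They also count participants too ill to attend Visits 15-16 under any rule.

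**Step 3. Precision**

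The half-width of a 95% interval for the mean paired change, in SDs of the change, is t(0.975, n − 1)/√n. The 95% level is assumed.

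- n = 20: 2.093/4.472 = 0.468
- n = 19: 2.101/4.359 = 0.482, wider by 3.0%
- n = 18: 2.110/4.243 = 0.497, wider by 6.3%

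**Step 4. Selection**

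If k participants are lost and their mean change differs by D from that of the others, the completers' mean differs from the mean of all 20 by (k/20) × D. With k = 1 and D = 1 SD (assumed, and large), the shift is 1/20 = 0.05 SD. That is 0.05/0.468 = 11% of the half-width.

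**The case against.** The strongest objection concerns cause. Visit 15 and the repeat biopsy are defined as following completion of heat. Someone who stops heat early does not reach them as written, whatever II.L says. This stands. A reader might infer that the II.L sentence by itself loses both primary values for any event during the heat course. The documents support that only for the short window after session 12, and the fix must therefore reach II.B and II.E as well.

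Second, the pilot is meant to estimate the effect of a 12-session course. A fasting glucose taken after a Grade 4 event and a shortened course may reflect acute illness or its treatment. Sparing such a participant another fast, glucose load and biopsy is also a cautious choice. This is a fair argument about which effect to estimate. It is met by making the visits conditional on safety and agreement, and by showing results both ways.

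Third, the PI already has discretion after each adverse event. That text concerns whether the study procedure continues. It does not provide for follow-up or soften the unconditional sentence on serious events.

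Fourth, a reader might infer that safety information is lost or the participant abandoned. The documents do not show this. II.L requires review and reporting, III.H provides follow-up care for research injury, and institutional policies not shown may require follow-up to outcome. What remains is a lack of explicit wording.

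Fifth, V.A has no rule for a missing post-treatment value. That gap applies to any dropout, and this sentence does not cause it. The mixed model mentioned there cannot recover a value that was never measured.

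**Conclusion.** The point holds as a cheap improvement of minor severity. The sentence removes participants from the study where stopping heat would do, and in most of the affected period it acts jointly with the visit definitions in II.B and II.E.

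The consequence is small. II.F describes a serious event as unlikely and sets temperature and heart-rate limits. Each event costs at most one pair, there is no powered hypothesis to damage, and even a large assumed difference moves the mean by about a tenth of the interval's half-width. The 10% to 64% range rests wholly on assumed risks of 0.5% to 5%, and the documents give no support for the upper end. A conclusion that the primary results would be materially biased is therefore not warranted. Selective loss arises mainly for events caused by heat, which are only some of those counted.

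**What to change.** - **II.L:** replace the sentence with wording such as: *A serious adverse event permanently stops heat treatment. The participant stays in the study, the event is followed until it resolves or stabilises and its outcome is recorded, and Visits 15-16 are completed where the PI judges this safe and the participant agrees; the biopsy may be omitted.*
- **II.B and II.E:** state that the post-intervention evaluation takes place after completion or permanent discontinuation of heat.
- **V.A:** show the paired results with and without participants who permanently stopped heat early or had a serious event. A split at fewer than 12 sessions would be too broad, because it would also set aside someone who missed one session for a trivial reason.

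The cost is about two sentences in II.L, a phrase each in II.B and II.E, and one sentence in V.A. Visits 15-16 are already planned for everyone.

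There are three downsides. Some post-treatment values will reflect incomplete exposure or acute illness. The IENF pair may still be lost if the biopsy is omitted. Following an event to its outcome may need staff contact beyond the 11-13 week timeline.

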## **III.** Subject Participation

#### A. Recruitment:

 Participants will be recruited for this study through flyers posted at the University of Kansas Medical Center, in the community, and electronically via websites and email (included in appendix). Subjects may also be recruited from Drs. [name]'s and [name]'s clinics. [name] will utilize the KU Diabetes Institute to identify potential participants from ongoing research studies. We will also utilize the Frontiers Research Participant Registry after approval from the Data Request Committee (DRC). Participants will be offered a \$25 for completing Visits 1, 2, 15 and 16; and \$15 for completing Visits 3-14; via ClinCard after completing each of the visits (\$280 total) to aid with time and transportation.

- [name] and [name] will perform the majority of recruitment. Individual mailings and phone calls will be made to applicable subjects from the Frontier's Research Participant Registry.
- 3. Attached.
- 4. Attached.

## **B.** Screening Interview/questionnaire: Attached.

## C. Informed consent process and timing of obtaining of consent

- 1 PIs and/or study coordinators authorized to review Informed Consent
- 2 Subjects will be given a copy of the consent form when their first visit (pre-intervention evaluation) is scheduled. This will give them ample time to review and prepare questions for the study team before their visit. The consent form will be reviewed with the subject by the PI and/or study coordinator in a private room at the CTSU at the start of their first visit. The subject will have the opportunity to ask any and all questions to the coordinator, or an investigator if requested, before signing. A signed copy will be given back to the subject.
- 3 All subjects should be English speaking, of consenting age (> 18 years old) and of sound mind (no cognitive or decisional impairment). If there is any question of this, the study coordinator will have an investigator assess ability to consent.
- D. Alternatives to Participation: The consent form includes the following statement: "Research is voluntary, and you may change your mind at any time. There will be no penalty to you if you decide not to participate, or if you start the study and decide to stop early. Either way, you can still get medical care and services at the University of Kansas Medical Center (KUMC).

The consent form explains what you have to do if you are in the study. It also describes the possible risks and benefits. Please read the form carefully and ask as many questions as you need to, before deciding about this research.

You can ask questions now or anytime during the study. The researchers will tell you if they receive any new information that might cause you to change your mind about participating."

- **E. Costs to Subjects:** There will be no cost to the subject for participation in the study, including all labs and procedures.
- **F.** How new information will be conveyed to the study subject and how it will be documented: [name], [name] and [name] will review screening results (laboratory) with subject only to assess eligibility for continuation. Drs. [name] or [name] will further discuss screening results with the subject by request.
- **G.** Payment, including a prorated plan for payment: Participants will be offered a \$40 for completing Visits 1, 2, 15 and 16; and \$20 for completing Visits 3 14; via ClinCard after

completing each of the visits (\$400 total) to aid with time and transportation. Subjects will not continue to receive payments after they've withdrawn from the study.

H. Payment for a research-related injury: We will include the following text in the consent form: "If subjects have a serious side effect or other problem during this study, they should immediately contact [name] at [contact]. If it is after 5:00 p.m., a holiday or a weekend, subjects should call [contact] [24-hour phone number], and this number will contact [name]. A member of the research team will decide what type of treatment, if any, is best for them at that time. If the subjects have a bodily injury as a result of participating in this study, treatment will be provided for them at the usual charge. Treatment may include first aid, emergency care and follow-up care, as needed. Claims will be submitted to their health insurance policy, their government program, or other third party, but they will be billed for the costs that are not covered by the insurance. The subjects do not give up any legal rights by signing this form."

## **IV.** Data Collection and Protection

#### A. Data Management and Security:

- 1. [name], [name], [name], [name], [name], [name]
- 2. Following a phone call pre-screening, potential subjects will be emailed or mailed the consent form prior to the first visit and the consent discussion. Pre-screening data will be securely kept via RedCAP. Consent forms will be kept in a separate folder from subject study worksheets, and kept in a secure, locked location at the University of Kansas. All subject study worksheets, labs, and biopsies will be de-identified and marked only with a subject ID. This information will be kept for 15 years according to the KUMC Records Retention Policy.
- 3. Through coded information.
- 4. Only the study team will have access to the key to the code.
- 5. Subjects will be assigned a study ID and this number will be used to follow subjects throughout the study. Only the consent forms (housed separately from the study worksheets) will be able to link identifiable data to study IDs.
- 6. Paper data (consents, study worksheets) will be stored in a designated and locked storage cabinet, to be overseen by the PI, co-Is, and study coordinators. No one except for the study team will have access to the storage cabinet. Electronic data will be stored on a KUMC-supported network drive (S- or P-drive) and in a RedCAP database.
- 7. N/A
- 8. N/A
- **B. Sample / Specimen Collection:** Blood will be collected at the CTSU by nursing staff and analysis of blood samples will be performed externally my Quest Diagnostics.
- C. Tissue Banking Considerations: N/A
- **D. Procedures to protect subject confidentiality**: Subject confidentiality will not be at risk during any time in the study.

## E. Quality Assurance / Monitoring

- 1. The data to be collected in this study will be reviewed in a timely fashion by the study team. We will provide self-assessments on a regular basis to determine that the data values are within normative values.
- 2. No

# V. Data Analysis and Reporting

- **A. Statistical and Data Analysis:** To understand how heat therapy impacts glucose control and sensory function in prediabetic patients with or without neuropathy, we compare pretreatment versus end-of-treatment measures of fasting glucose and neuropathy measures using intraepidermal nerve fiber (IENF) density as our two primary outcome measures. We will also make comparisons between secondary outcome measures such as the Utah Early Neuropathy Scale (UENS), Quantitative Sensory Testing (QST), blood and metabolic biomarkers. As pre- and post-treatment measurements are available for each patient, a twosided paired t-test will be used to test the null hypothesis of no difference in conductance between pre- and post- conductance measures. As the paired t-test assumes normally distributed data and because of the modest number of subjects in this pilot study (e.g., N =20), we will also explore the use of non-parametric methods for testing the aforementioned null hypothesis, such as a Wilcoxon signed-rank tests and/or a randomized-based test. We will also introduce variables for key clinical characteristics of the patient (e.g., patient age, sex, ethnicity, disease severity, etc.) into the linear mixed effects model and formally statistically test whether there is a significant interaction between these variables and time. In other words, if there a significant relationship between the temporal trajectory of conductance over the course of treatment and patient age at baseline.
- **B. Outcome**: The hypothesis will test whether prediabetic patients with or without neuropathy exhibit any improvements in metabolic symptoms and peripheral nerve mitochondria, leading to improvements in sensory function, via heat shock protein induction.
- **C. Study results to participants**: Laboratory results and medical evaluations will be given to the subject if they request it.
- **D. Publication Plan**: Data from this intervention will be published by Drs. [name], [name], [name], and [name] in appropriate journals, likely focusing on diabetes and/or neuropathy and pain. Publications will be developed in a timely fashion and are the responsibility of the PI and co-Is.

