## D. Subject Criteria (See Vulnerable Populations appendix, if applicable):

1. Inclusion criteria: Subjects will include both males and females, ages 45-75, that have suspected or diagnosed prediabetes with or without neuropathy (to be confirmed at pre-intervention evaluation).

- 2. Exclusion criteria: (1) skin conditions, circulatory insufficiency, or open wounds in the leg that would interfere with healing from a biopsy;
  - (2) stroke or other significant nervous system pathology;
  - (3) lidocaine allergy;
  - (4) anticipated difficulty with blood clotting due to disorder or use of a blood thinner such as Coumadin, Xarelto, or Eliquis;
  - (5) use of any medication used to treat abnormal blood glucose such as Metformin;
  - (6) body weight > 350 lbs.;
  - (7) history of anemia or vitamin b12 deficiency;
  - (8) clinical anemia (hematocrit <32 for women, <36 for men);
  - (9) abnormal SPEP result;
  - (10) history of cancer or chemotherapy treatment;
  - (11) current or recent use (within the last 6 months) of artificial fingernails / nail enhancements that would interfere with quantitative sensory testing;

(12) no special classes of subjects such as fetuses, neonates, pregnant women, prisoners, institutionalized individuals, non-English speaking individuals, or other who may be considered vulnerable populations will be included in this study.

- 3. Withdrawal/Termination criteria: Prediabetes will be determined using the American Diabetes Association (ADA) Diabetes Management Guidelines. The subject will meet the criteria for a diagnosis of pre-diabetes if the subject has one or more positive test(s) for either A1c (5.7-6.4%), fasting glucose (100-125 mg/dl), or 2-hr oral glucose tolerance test (140-199 mg/dl). If at pre-intervention evaluation, the subject does not meet the criteria for prediabetes (lower than the above-mentioned range), meets the ADA criteria for diabetes (higher than the above-mentioned range), the subject will be considered a screen fail and will not progress to skin biopsy or intervention.
- 4. Subject may participate in other observational studies but cannot participate in other studies in which they receive an intervention.

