  - a. Potential benefits for individuals including learning new information based on laboratory testing and medical examination, at no cost to the subject. This information may be of use to the participant and their physician by providing updated information on important parameters of prediabetes and/or neuropathy. Subjects will have the opportunity to receive heat therapy, which may offer multiple health benefits related to the cardiovascular system and metabolic health. Physiological benefits to the cardiovascular system in healthy subjects has been documented and those studies were performed by [name], from the University of Oregon. In addition, quality of life improvements have commonly been reported by patients undergoing chronic heat exposure (e.g. hot tub, sauna, etc.).
  - b. The information gained in this research study will be useful in developing novel treatments of peripheral neuropathy in the future related to prediabetes patients.
  - c. The proposed research will be helpful to develop fundamental knowledge about treatment approaches that will help reduce the burdens of disease and disability. This knowledge should offset the very minor risk to participation by individual subjects, given the protections that are in place and the low likelihood of a serious adverse event in this study.

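### After screening, and for the neuropathy examinations, results reach participants only through an on-request rule with no exception for clinically important findings

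*Combined protocol and SAP*

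**What the plan says.** Three sections bear on what participants are told.

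- **V.C, study results to participants:** "Laboratory results and medical evaluations will be given to the subject if they request it". Normal and abnormal findings are not distinguished.
- **III.F, conveying new information:** named study staff "will review screening results (laboratory) with subject only to assess eligibility for continuation". Study physicians "will further discuss screening results with the subject by request".
- **II.F.5.a, potential benefits:** "Potential benefits for individuals including learning new information based on laboratory testing and medical examination, at no cost to the subject". It continues: "This information may be of use to the participant and their physician by providing updated information on important parameters of prediabetes and/or neuropathy".

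Section II.D sets the limits that make a laboratory result disqualifying. A subject who "meets the ADA criteria for diabetes (higher than the above-mentioned range), the subject will be considered a screen fail". Hematocrit below 32 for women or 36 for men, and an abnormal SPEP, are exclusions (8) and (9). Screen failure means no biopsy and no heat treatment; no notification or referral step is attached to it.

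Under II.E.2, Visit 15 repeats the Visit 1 fasting laboratory tests and glucose tolerance test, and Visit 16 repeats the Visit 2 neuropathy examination.

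**The concern.** A rule that works only on request assumes that the participant has reason to ask. Someone whose fasting glucose has moved into the diabetes range during the study has no reason to suspect it. The treated participants are those for whom this is plausible: they qualify with values just below that range (A1c 5.7-6.4%, fasting glucose 100-125 mg/dl or 2-hour glucose 140-199 mg/dl), and exclusion (5) means that they enter without glucose-lowering medication. The study team will hold the result in any case, because V.A makes fasting glucose one of the two primary outcomes.

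At stake is participant protection, and whether the benefit offered in II.F.5.a is delivered. Section II.E.3 says that all procedures are for research and none is standard of care, so the text shows no parallel clinical route by which a finding would reach the participant's own physician.

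**Working it through.** The plan gives no figure on this point and no formula applies. The check is to match each set of results to the disclosure rule that governs it.

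| Results | Unprompted disclosure | On request |
|---|---|---|
| Visit 1 laboratory tests | III.F, for eligibility only | III.F (further discussion), V.C |
| Visit 2 neuropathy examination | None stated | V.C |
| Visit 15 laboratory tests and glucose tolerance test | None stated | V.C |
| Visit 16 neuropathy examination | None stated | V.C |

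**Visit 1.** Diabetes-range values, low hematocrit and abnormal SPEP all decide eligibility under II.D, so at screening they fall within the III.F review. What remains on request is the further discussion with a physician.

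**Visit 2.** III.F limits the unprompted review to laboratory results. Subjects qualify with or without neuropathy, so finding it for the first time changes no eligibility decision and triggers no stated disclosure.

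**Visits 15 and 16.** No eligibility decision remains, so III.F does not reach these results. V.C is the only rule left.

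**Other provisions that might fill the gap:**

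- The finger stick before and after the glucose tolerance test (II.E.2) checks glucose safety on the day. It does not act on the laboratory report.
- IV.E has the study team review data and check values against norms. It is a quality-assurance step and states no follow-up with the participant.
- II.L has the PI or co-investigators monitor and grade adverse events monthly, with nursing observation and calls from participants as sources. It does not say that out-of-range laboratory reports are screened as possible adverse events, and it contains no step for informing the participant of a result.

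**Reach.** Three evaluations (Visits 2, 15 and 16) for 20 treated participants gives at most 3 × 20 = 60 sets of results governed by V.C alone. The documents give no rate of clinically important findings, so no expected count follows.

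**The case against.** The strongest reply is that V.C gives participants a right to their results and forbids nothing. Study physicians carry out the Visit 2 and Visit 16 examinations face to face and may well say what they find. The study team also reviews data under IV.E and adverse events under II.L. The consent pages are not in the text available and may contain a statement about abnormal results.

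Much of this stands, and it rules out several stronger readings.

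- A reader might infer that people who fail screening for diabetes-range glucose, anemia or abnormal SPEP are not told unless they ask. III.F does not support that: screening laboratory results are reviewed with the subject without a request, and these findings are the reason for stopping.
- A reader might infer that V.C contradicts the benefit section. II.F.5.a speaks of potential benefits and of information that may be of use. Information available on request still fits those words, so this is a tension and not a contradiction.
- A reader might infer that nobody looks at out-of-range values. IV.E and II.L do assign review. What they lack is a step from an abnormal value to the participant.

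The reply does not supply a written rule for findings after screening or on examination. Permission to speak is not a procedure, and a team following V.C as written could leave such a finding unreported.

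**Conclusion.** The point holds for the Visit 15 laboratory tests and glucose tolerance test and for the Visit 2 and Visit 16 examinations. There the on-request rule stands alone and makes no exception for a result beyond the II.D limits or for newly found or worsened neuropathy. For screening laboratory results the gap is narrower: the result is reviewed with the subject, but only for eligibility, and no communication or referral step is written.

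It concerns up to 20 treated participants. It touches no endpoint, estimate or test, and how often it would matter cannot be derived from the documents. It is still worth correcting, because it is a stated rule with a participant-safety consequence and is cheap to change.

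The conclusion rests on two assumptions. One is that Visit 15 repeats the full Visit 1 laboratory list, including A1c, blood count and SPEP, which is the natural reading of II.E.2. The other is that no disclosure statement in the consent form already covers these results.

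**What to change.** Reconcile III.F, V.C and II.F.5.a so that they state one procedure:

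1. An investigator reviews and signs the Visit 1 and Visit 15 laboratory reports and the Visit 2 and Visit 16 examination findings.
2. Laboratory results beyond the protocol's own II.D limits (diabetes-range glucose or A1c, the hematocrit limits, abnormal SPEP), and examination findings that the investigator judges clinically important, are communicated to the participant by default for use with their own physician. Participants may opt out at consent.
3. All other results stay on request. A trigger based on any laboratory flag is not advised: in a cohort selected for raised glucose it could generate a notice for many participants.
4. New abnormalities after treatment are assessed under the existing adverse event process in II.L. They are not recorded as adverse events automatically.

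If the consent form already contains a disclosure statement, align V.C and III.F with it.

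The cost is a template letter or call and an investigator sign-off by existing staff, for the 20 treated participants and the screen failures, plus one sentence in the consent form. The procedure concerns communication only; what is done clinically about a finding is left to the participant and their physician.
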